- 4) Colonoscopy indication (Provation sites only, if available)
 - a) Screening
 - b) Surveillance
 - c) FOBT+
 - d) Other
 - e) Unknown
- 5) Bowel preparation quality (Provation sites only, if available)
 - a) Adequate vs. inadequate
 - b) Aronchick
 - c) Boston Bowel Preparation Score

Statistical Methods:

Colonoscopies performed on the day of CADe installation and the next 5 colonoscopies performed by each endoscopist after the date of installation (or matched date for control sites) will be excluded as a washout period to minimize training adaptation. For the 26 endoscopists who performed colonoscopies at multiple facilities, we will retain only procedures at the facility where they performed the largest number of colonoscopies.

Baseline data will be summarized as number (%), mean (\pm standard deviation) or median (interquartile range), as appropriate. For binary outcomes, we will estimate the association of CADe on study outcomes using mixed effects logistic regression (PROC GLIMMIX, SAS software, Cary, NC) with a random intercept for endoscopist and a random slope (at the endoscopist level) for study phase. We will also include fixed effects for group, phase, and a group by phase interaction (product term), with colonoscopy serving as the unit of analysis. The group by phase interaction is quantified as a ratio of odds ratios, where a coefficient greater than 1 for the interaction term (or 0 on the log-odds scale) reflects increased neoplasia detection in the post-deployment phase versus the pre-deployment phase in the CADe group compared to the non-CADe group. We will control for pre-randomization ADR stratum, patient demographics (e.g., sex, age, race, ethnicity, and rurality), and endoscopist information (e.g., specialty, sex, years since medical degree) in all analyses.

After estimating the association of CADe on adenoma detection, we will assess whether the effect was moderated by patient and endoscopist characteristics. We will fit additional models

for each potential moderator, adding a main effect for the moderator and interactions (product terms) with group, phase, and group by phase terms as fixed effects.

Withdrawal time information will only be available from the subset of VA facilities that use Provation MD software. As withdrawal time is a continuous variable, we will use a linear mixed effects regression model with the same predictors as described above. We will include only those colonoscopies without an associated pathology report and where cecal intubation was complete.

To assess whether the effect of CADe on ADR is moderated by endoscopist ADR quintile, endoscopists with at least 100 colonoscopies in the pre- and post-deployment phases each will be divided into quintiles based on pre-intervention ADR. The quintile variable will be entered into the model described above as a main effect and an interaction (product term) with the group, phase, and group by phase terms.

Computer Assisted Detection of Neoplasia during Colonoscopy Evaluation (CADeNCE)

Study Protocol Version 2.1

September 10, 2025

Evaluation Team:

[name], MHS
[name], MS, MEd
[name], PhD
[name]
[name], MPH

Summary of major revisions:

- 1) In addition to random intercepts for endoscopist and study phase in the regression models, a random intercept for facility was added as this was the unit of randomization

Background:

Colonoscopy is a key diagnostic and therapeutic procedure for the prevention of colorectal cancer (CRC) incidence and mortality. Central to colonoscopy's effectiveness is the identification and removal of colorectal neoplasia, including adenomatous polyps and sessile serrated lesions. The endoscopist's adenoma detection rate (ADR), classically defined as the proportion of screening colonoscopies in which one or more adenomas are detected, has been demonstrated to be strongly inversely associated with their patients' risk of post-colonoscopy colorectal cancer. Therefore, improving adenoma detection is a major target of quality assurance efforts.

The Veterans Health Administration's (VA) National Gastroenterology and Hepatology Program (NGHP) has embarked on a number of efforts to measure, monitor, and improve colonoscopy quality across the VA enterprise. One of these efforts is the VA Endoscopy Quality Improvement Program (VA-EQuIP) which is a collaboration between the VA Quality Enhancement Research Initiative (QUERI), the Office of Research and Development (ORD) and the NGHP. Investigators in the Measurement Science QUERI have developed processes for assessing the ADR of individual physicians and facilities through extraction of data from the Corporate Data Warehouse (CDW). Through collaboration with the VA Clinical Assessment Reporting and Tracking Program (CART), more detailed colonoscopy report information is available for 29 VA medical centers, with additional VA facilities expected to be added to the list soon. Overall, the VA ADR for colonoscopies of all indications is 47%¹, well above the benchmark of 30% for men undergoing screening colonoscopy.

In 2021, the FDA approved the first artificial intelligence (AI) system for computer assisted detection (CADe) of colorectal neoplasia. These CADe devices project an image on the endoscopy monitor (i.e., a bounding box) to alert the endoscopist to the presence of a suspected polyp within the colon. Initial studies, including randomized controlled trials, have demonstrated that use of CADe systems result in a significant improvement in adenoma detection, with a reduction in the miss rate of adenomas (i.e., fewer adenomas are found on a second colonoscopy when the first colonoscopy was performed with a CADe system compared to when the first colonoscopy did not use CADe).²⁻⁴ However, more recent studies have not demonstrated a clear benefit of these devices.^{5,6} Moreover, most of the additional adenomas that are detected are diminutive polyps, the vast majority of which are thought to be of minimal, if any, clinical significance. When multiple adenomas are detected during colonoscopy, current guidelines recommend repeating colonoscopy sooner than would otherwise be recommended. Also, the CADe systems may have unintended consequences, such as creating alert fatigue through false alarms or negatively impacting training of gastroenterology fellows.

Objective:

The NGHP planned to formally evaluate the quantitative and qualitative impact and outcomes of use of CADe within VA medical centers following the purchase and distribution to randomly selected gastrointestinal endoscopy units.

Setting:

Veteran Health Administration (VA) Medical Centers

Intervention:

As part of ongoing quality assurance efforts, the NGHP purchased 115 Medtronic GI Genius® CADe devices in late 2022. All facilities were sorted according to their facility-level ADR (for all indications) and categorized as below 30%, 30% to <40% or ≥40%. A random number generator was then used to sort the VA medical centers within each of these 3 ADR strata. Alternating facilities (i.e., approximately 50%) of facilities within the 2 lower ADR stratum were allocated the CADe devices. To assure equitable distribution of the remaining CADe devices across the 18 VA Integrated Service Networks (VISNs), the remaining devices were offered to randomly selected facilities (all within the ≥40% ADR stratum) such that each VISN had 2-3 facilities with CADe devices.

Upon identification of a potential site, the Gastroenterology Section Chief (or equivalent) at that randomly selected site was asked if they were interested in receiving the devices and if all endoscopists at their facility would agree to use the device during colonoscopy. The physicians were not mandated to use the devices but were asked to notify the NGHP if endoscopists were not routinely using the devices so that the devices could be reallocated to other VA facilities that would make use of the CADe devices. Upon receiving concurrence from facility endoscopy leadership, the devices were installed in all procedure rooms that are routinely used for colonoscopy at that facility. The devices were not installed on travel carts for emergency procedures. One facility did decline to receive the devices due to concerns that the devices would negatively impact efficiency in the endoscopy unit. That facility was replaced with another randomly selected VA medical center. Ultimately, 43 VA facilities received and installed the 115 CADe devices.

Survey: To assess the end-user experience, a Microsoft Forms electronic survey will be distributed to VA endoscopists who performed at least 25 colonoscopies between December 1, 2022 and May 31, 2023. Endoscopists will be invited via email with up to two follow-up reminders. Survey questions will address self-reported use of CADe for different colonoscopy indications, assessment of the benefits and negative impacts of CADe (e.g., impact on neoplasia detection or withdrawal time), and overall impression of CADe. Survey completion will be optional. Only staff gastroenterologists and surgeons will be eligible to complete the survey.

Oversight:

This quality assurance evaluation was conducted under the auspices of the VA NGHP. Evaluation of the quality of colonoscopy, including the effectiveness of CADe, was previously deemed to be quality assurance by the University of Utah and Salt Lake City VA Medical Center (IRB_00119922); a continuing review of this IRB with amendment was approved for evaluation of AI implementation in 2022. This quality assurance evaluation is registered with ClinicalTrials.gov (NCT05888623).

Database:

The VA Corporate Data Warehouse administrative and patient care data will be used to temporally link CPT codes for colonoscopy to pathology results to assess detection of neoplasia and other study outcomes. Natural language processing (NLP) with full-text indexing searches is used to classify pathology (i.e., adenoma, sessile serrated lesion, adenocarcinoma). Validation of this method to classify adenomas from the pathology results showed 99.5% accuracy.⁷ Separately, colonoscopy data from sites using Provation MD software (Provation, Minneapolis, MN) is exported to a national VA database for quality assurance purposes. This software includes information on colonoscopy quality, such as withdrawal time, indication, bowel preparation quality. Outcomes will be ascertained for colonoscopies performed between October 1, 2021 through June 30, 2023.

Outcomes:

Primary outcome: The primary outcome is the change in ADR from the pre- to post-deployment periods from colonoscopies performed with CADe available compared to colonoscopies performed where CADe was not available.

Secondary Outcomes:

- 1) Adenocarcinoma detection rate
- 2) Sessile serrated lesion detection rate
- 3) Proportion of colonoscopies where pathology specimens are obtained
- 4) Proportion of pathology without adenoma or adenocarcinoma
 - a) This serves as a surrogate for false positive lesion detection during use of CADe
- 5) Withdrawal time when no maneuvers are performed
 - a) Limited to Provation Sites
 - b) To assess the negative impact of CADe on procedure time or a possible Hawthorne effect.
- 6) Provider satisfaction with CADe for colonoscopy
- 7) Adenoma detection rate stratified by the endoscopist's pre-CADe ADR quintile

Additional analyses to be considered (due to data availability):

- 1) Bowel preparation quality
 - a) Limited to Provation sites
- 2) Number of polyps per colonoscopy
 - a) Limited to Provation sites
- 3) Size of polyps detected
 - a) Limited to Provation sites
- 4) Advanced neoplasia detection rates
 - a) Limited to Provation sites
- 5) Surveillance recommendations after colonoscopy

Independent Variables:

- 1) VA Facility characteristics
 - a) Pre-randomization adenoma detection rate

- 2) Patient characteristics
 - a) Age
 - b) Gender
 - c) Race
 - d) Ethnicity
 - e) Rurality
- 3) Provider characteristics
 - a) Specialty
 - b) Sex
 - c) Years since completion of medical training
- 4) Colonoscopy indication (Provation sites only, if available)
 - a) Screening
 - b) Surveillance
 - c) FOBT+
 - d) Other
 - e) Unknown
- 5) Bowel preparation quality (Provation sites only, if available)
 - a) Adequate vs. inadequate
 - b) Aronchick
 - c) Boston Bowel Preparation Score

Statistical Methods:

Colonoscopies performed on the day of CADe installation and the next 5 colonoscopies performed by each endoscopist after the date of installation (or matched date for control sites) will be excluded as a washout period to minimize training adaptation. For the 26 endoscopists who performed colonoscopies at multiple facilities, we will retain only procedures at the facility where they performed the largest number of colonoscopies.

Baseline data will be summarized as number (%), mean (\pm standard deviation) or median (interquartile range), as appropriate. For binary outcomes, we will estimate the association of CADe on study outcomes using mixed effects logistic regression (PROC GLIMMIX, SAS software, Cary, NC) with random intercepts for facility and endoscopist and random slopes (at the facility and endoscopist level) for study phase. We will also include fixed effects for group, phase, and a group by phase interaction (product term), with colonoscopy serving as the unit of analysis. The group by phase interaction is quantified as a ratio of odds ratios, where a coefficient greater than 1 for the interaction term (or 0 on the log-odds scale) reflects increased neoplasia detection in the post-deployment phase versus the pre-deployment phase in the CADe group compared to the non-CADe group. We will control for pre-randomization ADR stratum, patient demographics (e.g., sex, age, race, ethnicity and rurality), and endoscopist information (e.g., specialty, sex, years since medical degree) in all analyses.

After estimating the association of CADe on adenoma detection, we will assess whether the effect was moderated by patient and endoscopist characteristics. We will fit additional models

for each potential moderator, adding a main effect for the moderator and interactions (product terms) with group, phase, and group by phase terms as fixed effects.

Withdrawal time information will only be available from the subset of VA facilities that use Provation MD software. As withdrawal time is a continuous variable, we will use a linear mixed effects regression model with the same predictors as described above. We will include only those colonoscopies without an associated pathology report and where cecal intubation was complete.

To assess whether the effect of CADe on ADR is moderated by endoscopist ADR quintile, endoscopists with at least 100 colonoscopies in the pre- and post-deployment phases each will be divided into quintiles based on pre-intervention ADR. The quintile variable will be entered into the model described above as a main effect and an interaction (product term) with the group, phase, and group by phase terms.

References:

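### The false-positive surrogate (secondary outcome 4) counts pathology whose only lesion is a sessile serrated lesion, which secondary outcome 2 counts as a detection

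*Combined protocol and SAP*

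**What the plan says.** In Protocol Version 2.1, Outcomes, secondary outcome 4 is "Proportion of pathology without adenoma or adenocarcinoma". Its sub-item gives the purpose: "This serves as a surrogate for false positive lesion detection during use of CADe". Secondary outcome 2, in the same list, is "Sessile serrated lesion detection rate".

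The Background describes the effectiveness of colonoscopy as resting on "identification and removal of colorectal neoplasia, including adenomatous polyps and sessile serrated lesions". The Database section says natural language processing (NLP) "is used to classify pathology (i.e., adenoma, sessile serrated lesion, adenocarcinoma"), which makes SSL a class of its own. The only accuracy given concerns adenomas: "Validation of this method to classify adenomas from the pathology results showed 99.5% accuracy".

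Under Statistical Methods, "For binary outcomes, we will estimate the association of CADe on study outcomes using mixed effects logistic regression", "with colonoscopy serving as the unit of analysis". The effect is the group-by-phase interaction, expressed as a ratio of odds ratios. Outcome 4 has the same wording in Version 2.0, where it first appears.

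**The concern.** A surrogate for false positives should count tissue that turned out not to be what the device is meant to find. By the plan's own account an SSL is such a target, yet outcome 4 removes only adenoma and adenocarcinoma from its event. SSL-only pathology stays in and is scored as a false positive.

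This inflates the level of the surrogate. It can also distort the comparison: if CADe finds more SSL-only cases, the written measure can rise when no additional non-neoplastic tissue has been taken, or fail to show a real improvement in yield. The plan names unintended consequences of CADe as a reason for the evaluation, and this outcome is one of the few checks on them.

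**Working it through.** **Definitions side by side.** Consider a colonoscopy whose only classified lesion is an SSL.

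- Outcome 2: SSL present, so it is an event (a detection).
- Outcome 4: no adenoma and no adenocarcinoma, so it is an event (a false positive).

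The overlap would vanish only if adenoma were read to include SSL. The three-class NLP list and the separate SSL outcome rule that out, and no other section removes SSL-only pathology. SSLs found together with an adenoma or adenocarcinoma are unaffected.

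**Inputs for size.** The plan states no figure for outcome 4, so there is none to reproduce. Per 100 colonoscopies:

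- 47 with adenoma or adenocarcinoma: the stated all-indication ADR, used as a stand-in
- n = 20 with non-neoplastic tissue only: assumed
- s with SSL only: assumed 1, 3 or 5

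**Level.** As written: (s + n)/(47 + n + s). SSL excluded: n/(47 + n + s).

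| s | As written | SSL excluded | Overstatement | SSL-only share of counted false positives |
|---|---|---|---|---|
| 1 | 21/68 = 30.9% | 20/68 = 29.4% | 1.5 points | 1/21 = 5% |
| 3 | 23/70 = 32.9% | 20/70 = 28.6% | 4.3 points | 3/23 = 13% |
| 5 | 25/72 = 34.7% | 20/72 = 27.8% | 6.9 points | 5/25 = 20% |

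With s = 3, the SSL-only share is 3/13 = 23% if n = 10 and 3/33 = 9% if n = 30.

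**Change after deployment.** Start from s = 3, n = 20, and suppose every extra detection comes from a colonoscopy that previously had no specimen. Odds ratios are crude, with the control group unchanged. The base odds are 23/47 as written and 20/50 with SSL excluded.

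| Extra SSL-only | Extra adenoma | As written | Odds ratio | SSL excluded | Odds ratio |
|---|---|---|---|---|---|
| 1.5 | 0 | 24.5/71.5 = 34.3% | (24.5/47)/(23/47) = 1.07 | 20/71.5 = 28.0% | (20/51.5)/(20/50) = 0.97 |
| 1.5 | 3 | 24.5/74.5 = 32.9% | (24.5/50)/(23/47) = 1.00 | 20/74.5 = 26.8% | (20/54.5)/(20/50) = 0.92 |
| 0.3 | 0 | 23.3/70.3 = 33.1% | 23.3/23 = 1.01 | 20/70.3 = 28.4% | 50/50.3 = 0.99 |
| 0.3 | 1 | 23.3/71.3 = 32.7% | (23.3/48)/(23/47) = 0.99 | 20/71.3 = 28.1% | (20/51.3)/(20/50) = 0.97 |

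With non-neoplastic-only cases constant, the written measure rises only if the adenoma gain is below 47/(s + n) times the SSL-only gain: 47/23 = 2.0 here, 47/13 = 3.6 at n = 10 and 47/33 = 1.4 at n = 30.

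**Second set of assumptions.** Let P colonoscopies per 100 have pathology (60 to 75, assumed), with 47.5 neoplastic (47 plus an assumed 0.5 with adenocarcinoma only) and S with SSL only (1 to 6, assumed). Add one SSL-only case with new pathology. As written, the odds ratio is (P − 46.5)/(P − 47.5), from 13.5/12.5 = 1.08 at P = 60 to 28.5/27.5 = 1.04 at P = 75. With SSL excluded it is (47.5 + S)/(48.5 + S), about 0.98 throughout. The direction again reverses.

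**The case against.** The strongest reply is about consequence. The planned estimate is a group-by-phase ratio of odds ratios, so a level error shared by both groups and phases largely cancels. That stands: the level table describes the reported proportion, and only a differential change in SSL-only cases biases the contrast. The 1.5-point gain is also a 50% relative rise on the assumed base. With a 10% rise (0.3 points) the written and SSL-excluded odds ratios differ by only about 0.02, and with a 1-point adenoma gain they point the same way.

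The no-previous-specimen assumption matters too. If the extra SSLs turn up where only non-neoplastic tissue would otherwise have been sampled, the written figure stays at 23/70. But the SSL-excluded figure then falls to 18.5/70 = 26.4% (odds ratio (18.5/51.5)/(20/50) = 0.90), so the written measure misses an improvement.

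The redefinition depends on an SSL class of unstated accuracy. If it found 80% of SSL-only cases (assumed) with no false labels, the result would be (20 + 0.6)/70 = 29.4%, nearer to 28.6% than 32.9% is. Mislabelling non-neoplastic tissue as SSL works the other way. At that sensitivity, the redefinition is further from target than the present wording once specificity among the 20 falls below about 82% at s = 3 (20(1 − spec) − 0.6 > 3), or 94% at s = 1 (20(1 − spec) − 0.2 > 1). This limit is real, though outcome 2 already relies on the same class.

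Three further points stand in part. SSL-only cases cannot be recovered from outcomes 2 and 3, but they can be bounded, since they cannot exceed the SSL rate. Other non-neoplastic biopsies would still count after the fix, so outcome 4 remains a surrogate. A late redefinition can only lower the apparent false-positive level; reporting both proportions and dating the change answers that.

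**Conclusion.** The concern holds, and the definition of outcome 4 is wrong as written: it labels as false positive a lesion that the plan elsewhere treats as a target. This follows from the text alone and needs no assumed rate.

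The size is not known from the documents. Under the assumptions shown, the level is overstated by 1.5 to 6.9 points. The distortion of the contrast ranges from negligible, for a small SSL-only gain, to a reversal of direction (1.07 against 0.97) for a 1.5-point gain without more adenomas. The damage is confined to one secondary outcome. The per-pathology denominator is a legitimate yield measure and is not in question. The point should be fixed before outcome 4 is interpreted.

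**What to change.** - Define the outcome 4 event as pathology with no adenoma, no SSL and no adenocarcinoma, using the existing NLP classes.
- Keep the per-pathology denominator and state its unit: colonoscopies with linked pathology.
- Report the proportion as now worded beside it, labelled as such.
- Date the change and disclose that it was made after the data period. Data run to June 30, 2023; Version 2.1 is dated September 10, 2025.
- State the accuracy of the SSL class, or that it is not known.
- Optionally add a rate over all colonoscopies, described as burden rather than yield.

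The cost is a change of SAP wording and the recoding of one derived variable, with no new data. The drawbacks are a late change to a secondary outcome and reliance on a class whose accuracy is not stated.

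### Secondary outcome 4, the false-positive surrogate, appears to use procedures with pathology as its denominator, so if CADe raises adenoma detection it can stay flat or fall while more colonoscopies yield pathology without adenoma or adenocarcinoma

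*Combined protocol and SAP*

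**What the plan says.** In Protocol Version 2.1, under Outcomes, secondary outcome 3 is the "Proportion of colonoscopies where pathology specimens are obtained". The next item, outcome 4, is the "Proportion of pathology without adenoma or adenocarcinoma", with the note: "This serves as a surrogate for false positive lesion detection during use of CADe". Outcome 2 is the "Sessile serrated lesion detection rate". No other listed outcome is labelled as measuring false positives, and no version of outcome 4 over all colonoscopies is listed.

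Under Statistical Methods, binary outcomes are fitted by mixed effects logistic regression "with colonoscopy serving as the unit of analysis". On the effect measure the plan says: "The group by phase interaction is quantified as a ratio of odds ratios". It does not say whether outcome 4 is counted per colonoscopy with pathology, per report or per specimen. It also does not say how outcome 4 is to be interpreted if outcome 3 changes as well.

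**The concern.** Outcomes 3 and 4 sit next to each other and are worded differently: one is a share of colonoscopies, the other a share of pathology. The contrast suggests that the denominator of outcome 4 is procedures with tissue. Whether tissue is taken happens after deployment, and the plan treats it as an outcome that CADe may affect. Each additional colonoscopy with an adenoma enlarges the denominator of outcome 4 without entering its numerator, and raising adenoma detection is the effect that the primary outcome tests. A benefit on the primary outcome can therefore pull outcome 4 down.

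What is at stake is how a null or favourable result is read. The Background names false alarms as a possible unintended consequence. A ratio of odds ratios at or below 1 on outcome 4 could be reported as no increase in false positives when more colonoscopies ended with pathology but no adenoma or adenocarcinoma. In addition, conditioning on a post-deployment event compares subsets that CADe may have altered. Random allocation of facilities and the group-by-phase contrast deal with stable baseline differences, but not with selection that the device itself causes.

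**Working it through.** The plan gives no rate, power or expected effect for outcome 4, so there is no figure to reproduce. The check is direct arithmetic, counting per colonoscopy.

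**Inputs**
- A = share of colonoscopies with adenoma or adenocarcinoma. ADR serves as a proxy. From the Background: "Overall, the VA ADR for colonoscopies of all indications is 47" per cent.
- P = share of colonoscopies with pathology (outcome 3). The documents do not give it. Assumed 70%, varied from 60% to 80%.
- Direction of change in A: the Background cites initial studies in which "use of CADe systems result in a significant improvement in adenoma detection", but gives no size. The rises used below are assumptions.
- N = P − A = share of all colonoscopies with pathology but no adenoma or adenocarcinoma.

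**Formula**

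Outcome 4 = N/(A + N) = 1 − A/P, so its odds are N/A. It falls whenever N rises proportionally less than A, that is when ΔN/ΔA < N₀/A₀. The break-even ratio N₀/A₀ is 13/47 = 0.28 at P = 60%, 23/47 = 0.49 at 70% and 33/47 = 0.70 at 80%.

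**ADR 47% to 50%, starting P = 70%**
- Before: N = 70 − 47 = 23; outcome 4 = 23/70 = 32.9%.
- P rises to 74.5%: N = 24.5; outcome 4 = 24.5/74.5 = 32.9%, unchanged; N is up 15 per 1,000.
- P rises to 74%: N = 24; outcome 4 = 24/74 = 32.4%, lower; N is up 10 per 1,000.

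**Rise in N that leaves outcome 4 unchanged, ADR 47% to 50%**

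ΔN = N₀ × (50/47 − 1) = N₀ × 3/47.

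| Assumed starting P | N₀ | Outcome 4 | New P | New N | Rise per 1,000 |
|---|---|---|---|---|---|
| 60% | 13.0% | 21.7% | 63.8% | 13.8% | 8 |
| 70% | 23.0% | 32.9% | 74.5% | 24.5% | 15 |
| 80% | 33.0% | 41.3% | 85.1% | 35.1% | 21 |

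**On the plan's effect scale** (starting P = 70%; simple marginal odds, assuming no change in the control group)

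| Assumed change in A, N (points) | Outcome 4 | Its ratio of odds ratios | N over all colonoscopies | Its ratio of odds ratios |
|---|---|---|---|---|
| +5, +2 | 32.86% to 32.47% | (25/52)/(23/47) = 0.982 | 23% to 25% | (25/75)/(23/77) = 1.116 |
| +5, +3 | 32.86% to 33.33% | (26/52)/(23/47) = 1.022 | 23% to 26% | (26/74)/(23/77) = 1.176 |
| 0, +1 | 32.86% to 33.80% | (24/47)/(23/47) = 1.043 | 23% to 24% | (24/76)/(23/77) = 1.057 |

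In the first row the two measures point in opposite directions. In the second they agree in direction, but outcome 4 is much closer to 1. In the third, with no change in ADR, they agree.

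**The case against.** Five points on the other side have weight.

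- **The counting unit is not stated.** The wording does not mention reports, and colonoscopy is the unit of analysis. This stands as a limit on the reading. The contrast with outcome 3 still makes procedures with pathology the natural denominator, and if all colonoscopies were meant, the wording needs correcting anyway.
- **The change can be inferred from planned outcomes.** In the first example outcome 3 rises by 45 per 1,000 and ADR by 30; the difference is the 15. If outcome 4 is counted per colonoscopy, outcome 3 times outcome 4 gives the same share (0.745 × 0.329 = 0.245). This stands for rough point estimates. The separate ratios of odds ratios for those outcomes do not combine into the ratio needed, nor into its interval.
- **The present ratio is a legitimate estimand.** It is a false-discovery proportion among procedures with tissue, and a flat value correctly says that yield has not changed. This stands, and is a reason to keep it. It does not tell whether more patients overall are affected.
- **Masking needs ADR to rise.** The Background notes that more recent studies show no clear benefit. This also stands: without an ADR effect, outcome 4 moves the right way.
- **The examples are constructed.** The range of 8 to 21 per 1,000 is solved so that outcome 4 stays constant. It shows what is possible and does not estimate a likely bias.

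A reader might infer that the extra cases are resections of non-neoplastic tissue only. The documents do not support that. Outcome 3 counts specimens, which may include biopsies, and the numerator of outcome 4 keeps cases with only a sessile serrated lesion, which the Background groups with neoplasia and outcome 2 treats as a detection target.

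**Conclusion.** The point holds as a conditional one about interpretation. On its natural reading, outcome 4 has a denominator that CADe can change. If adenoma detection rises, outcome 4 can be flat or lower while a larger share of all colonoscopies have pathology without adenoma or adenocarcinoma. With ADR going from 47% to 50%, an unchanged outcome 4 is compatible with a rise of about 15 per 1,000 at an assumed pathology rate of 70%, and about 8 to 21 per 1,000 at 60% to 80%. Only the 47% comes from the documents. The pathology rates and the 3-point rise are assumptions, and ADR stands in for adenoma or adenocarcinoma.

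A reader might go further and conclude that outcome 4 is invalid, that the plan conceals this change, or that outcome 4 should be replaced. None of these follows. It is a valid yield measure, outcome 3 and ADR partly disclose the change, and it has been prespecified since Version 2.0. What is missing is a modelled contrast, with an interval, for the share of all colonoscopies. Adding it is a cheap improvement to a secondary outcome; the primary analysis is not affected.

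**What to change.** 1. State that outcome 4 is counted per colonoscopy, with colonoscopies that have pathology as its denominator.
2. Keep it as prespecified, and describe it as a yield (false-discovery) proportion among procedures with pathology.
3. Add the proportion of all colonoscopies in which pathology was obtained and showed no adenoma or adenocarcinoma. Use the same numerator as outcome 4 and the same group-by-phase mixed model, and label it a late supplementary analysis.
4. Report the two together with outcome 3 and ADR, and do not conclude from outcome 4 alone that false positives did not increase.

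The cost is a line or two of wording and one more run of an existing model on data already linked. The downside is one further secondary analysis, added after the ascertainment period ended on June 30, 2023. The added measure also has limits of its own. It misses non-neoplastic tissue removed from patients who also have an adenoma, and it still counts cases with only a sessile serrated lesion.
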